5.4 Pathology and Imaging Correlation

As part of standard care, lymph nodes mapped on MR imaging may be resected during at the time of surgery or may be biopsied via core needle technique or fine needle aspiration. Resected nodes will be named and numbered based on their location in diagrammatic maps obtained from MR images. Multiple sections of resected or biopsied lymph nodes will be stained with hemotoxylin and eosin and the slides will be reviewed by NCI pathologists. The histopathology results will be compared with signal intensity change amounts between unenhanced, 24 and 48 hours post Ferumoxytol infusion T2*W MR images. No samples will be obtained or stored on this protocol other than in the Pathology Department, NCI, NIH.

Patients who do not undergo surgical excision or biopsy of the lymph nodes will be followed (per treatment protocol) for a minimum of 12 months. During this follow up, conventional images (e.g. CT, MRI) will be evaluated and RECIST 1.1 criteria will be used for assessment of metastatic involvement for correlation of Ferumoxytol enhanced MRI findings.

6 SAFETY REPORTING REQUIREMENTS/DATA AND SAFETY MONITORING PLAN

6.1 Definitions

6.1.1 Adverse Event

An adverse event is defined as any reaction, side effect, or untoward event that occurs during the course of the clinical trial associated with the use of a drug in humans, whether or not the event is considered related to the treatment or clinically significant. For this study, AEs will include events reported by the patient, as well as clinically significant abnormal findings on physical examination or laboratory evaluation. A new illness, symptom, sign or clinically significant laboratory abnormality or worsening of a pre-existing condition or abnormality is considered an AE. All AEs must be recorded on the AE case report form unless otherwise noted above in Section **5.1**.

All AEs, including clinically significant abnormal findings on laboratory evaluations, regardless of severity, will be followed for 48 hours after dose infusion. AEs should be reported up to 30 days following the last dose of study drug.

6.1.2 Suspected adverse reaction

Suspected adverse reaction means any adverse event for which there is a reasonable possibility that the drug caused the adverse event. For the purposes of IND safety reporting, 'reasonable possibility' means there is evidence to suggest a causal relationship between the drug and the adverse event. A suspected adverse reaction implies a lesser degree of certainty about causality than adverse reaction, which means any adverse event caused by a drug.

6.1.3 Unexpected adverse reaction

An adverse event or suspected adverse reaction is considered "unexpected" if it is not listed in the investigator brochure or is not listed at the specificity or severity that has been observed; or, if an investigator brochure is not required or available, is not consistent with the risk information described in the general investigational plan or elsewhere in the current application. "Unexpected", also refers to adverse events or suspected adverse reactions that are mentioned in the investigator brochure as occurring with a class of drugs or as anticipated from the pharmacological properties of the drug, but are not specifically mentioned as occurring with the particular drug under investigation.

6.1.4 Serious

An Unanticipated Problem or Protocol Deviation is serious if it meets the definition of a Serious Adverse Event or if it compromises the safety, welfare or rights of subjects or others.

6.1.5 Serious Adverse Event

An adverse event or suspected adverse reaction is considered serious if in the view of the investigator or the sponsor, it results in any of the following:

- Death,
- A life-threatening adverse drug experience
- Inpatient hospitalization or prolongation of existing hospitalization
- Persistent or significant incapacity or substantial disruption of the ability to conduct normal life functions
- A congenital anomaly/birth defect.
- Important medical events that may not result in death, be life-threatening, or require hospitalization may be considered a serious adverse drug experience when, based upon appropriate medical judgment, they may jeopardize the patient or subject and may require medical or surgical intervention to prevent one of the outcomes listed in this definition.

6.1.6 Disability

A substantial disruption of a person's ability to conduct normal life functions.

6.1.7 Life-threatening adverse drug experience

Any adverse event or suspected adverse reaction that places the patient or subject, in the view of the investigator or sponsor, at immediate risk of death from the reaction as it occurred, i.e., it does not include a reaction that had it occurred in a more severe form, might have caused death.

6.1.8 Protocol Deviation (NIH Definition)

Any change, divergence, or departure from the IRB-approved research protocol.

6.1.9 Non-compliance (NIH Definition)

The failure to comply with applicable NIH Human Research Protections Program (HRPP) policies, IRB requirements, or regulatory requirements for the protection of human research subjects.

6.1.10 Unanticipated Problem

Any incident, experience, or outcome that:

• Is unexpected in terms of nature, severity, or frequency in relation to

(a) the research risks that are described in the IRB-approved research protocol and informed consent document; Investigator's Brochure or other study documents, and

(b) the characteristics of the subject population being studied; AND

- Is related or possibly related to participation in the research; AND
- Suggests that the research places subjects or others at a greater risk of harm (including physical, psychological, economic, or social harm) than was previously known or recognized.

6.2 NCI-IRB and NCI Clinical Director (CD) Reporting

6.2.1 NCI-IRB and NCI CD Expedited Reporting of Unanticipated Problems and Deaths

The Protocol PI will report in the NIH Problem Form to the NCI-IRB and NCI Clinical Director:

- All deaths, except deaths due to progressive disease
- All Protocol Deviations
- All Unanticipated Problems
- All non-compliance

Reports must be received within 7 days of PI awareness via iRIS.

- 6.2.2 NCI-IRB Requirements for PI Reporting of Adverse Events at Continuing Review
 - 1. A summary of all protocol deviations in a tabular format to include the date the deviation occurred, a brief description of the deviation and any corrective action.
 - 2. A summary of any instances of non-compliance
 - 3. A tabular summary of the following adverse events:
 - All Grade 2 **unexpected** events that are possibly, probably or definitely related to the research;
 - All Grade 3 and 4 events that are possibly, probably or definitely related to the research;
 - All Grade 5 events regardless of attribution;
 - All Serious Events regardless of attribution.

NOTE: Grade 1 events are not required to be reported.

6.3 Data and Safety Monitoring Plan

6.3.1 Principal Investigator/Research Team

This study will not have a formal data safety monitoring plan (DSMP), however, the Principal Investigator and Lead Associate Investigator will re-evaluate the protocol after each patient.

All data will be collected in a timely manner and reviewed by the principal investigator or a lead associate investigator. Adverse events will be reported as required above. Any safety concerns, new information that might affect either the ethical and or scientific conduct of the trial, or protocol deviations will be immediately reported to the IRB using iRIS.

The principal investigator will review adverse event data on each patient to ensure safety and data accuracy. The principal investigator will personally conduct or supervise the investigation and provide appropriate delegation of responsibilities to other members of the research staff.

7 STATISTICAL CONSIDERATIONS

7.1 Study Design/Endpoints

- This is an open-label, single-center study. Fifty evaluable subjects in three different arms (30 in arm 1 and 10 in arms 2 and 3) will be enrolled into the study.
- The primary objective is to compare the difference in signal between metastatic and normal nodes in prostate, kidney and bladder cancer patients.
- For determining the difference in signal between metastatic and normal nodes patients will be infused 7.5mg/kg Fe dose of Ferumoxytol.
- Subjects with documented prostate or bladder or kidney cancer will undergo preinfusion and 24, 48 hours post-Ferumoxytol infusion MRI consisting of T1 weighted (W), T2W and T2*W MRI at 3 Tesla (T) magnet.
- The difference in signal between metastatic and normal nodes will be determined by measuring the difference in signal between tumor and normal node, and determining the maximum difference per each imaging time point.
- Patients will also undergo ultrasound examination pre-infusion and 24, 48 hours post-Ferumoxytol infusion time points. The signal changes at post-infusion ultrasound will be visually evaluated in an exploratory manner.

7.2 Sample Size/Accrual Rate

Thirty evaluable patients in 3 different arms (arm1=prostate cancer, arm 2=bladder cancer, arm 3=kidney cancer) will be included in this trial with an accrual rate of 1-2 patients a month. A patient will be evaluable if he/she completes pre and 24 hours, 48 hours post ferumoxytol infusion MRI scans and may undergo surgical excision of the lymph node dissection or needle biopsy of the lymph node or completes the clinical assessment including conventional imaging evaluation. In order to allow for the possibility of a small number of inevaluable patients, the accrual ceiling will be set least 56. Therefore, it is expected that this study will be completed within 2 years.

7.3 Stratification Factors

• Arm 1

- Subject must have a documented diagnosis of prostate cancer with evidence of lymph node involvement (with a short axis diameter of ≥1.5cm)
- Arm 2
 - Subject must have a documented diagnosis of bladder cancer (transitional cell carcinoma) with evidence of lymph node involvement (with a short axis diameter of ≥1.5cm)
- Arm 3
 - Subject must have a documented diagnosis of kidney cancer (all types of renal cell cancer) with evidence of lymph node involvement (with a short axis diameter of ≥1.5cm)

All patients will receive a dose of 7.5mg/kg Fe Ferumoxytol.

7.4 Analysis of Primary Endpoint

The primary objective of the ferumoxytol study is to compare the difference in pre-post ferumoxytol infusion signal change between metastatic and normal nodes in prostate, kidney and bladder cancer patients. Based on the previous study (Neoplasia, 2007), the mean signal drop of benign lymph nodes was 6.3. In comparison, most of the malignant nodes showed little change in signal with mean signal drop equal to 0.63. The standard deviation of signal change was similar for benign and malignant nodes and equaled 1.7 approximately.

Each patient is expected to have at least 1-2 benign lymph nodes and 1-2 metastatic nodes. For the purpose of sample size calculation, we use the conservative assumption that each patient has only one benign and one metastatic node and there is no correlation between benign lymph and metastatic node in pre-post ferumoxytol infusion signal change. With 10 patients for each cancer, the study has 93% power to detect a minimal mean signal change of three with the two-sided paired t-test at the 5% significance level. The power will increase if each patient has signals observed in multiple benign lymph nodes and metastatic nodes, as well as if the signal changes in benign and metastatic node are positively correlated. Thus, a total of 30 patients, 10 for each cancer are sufficient to achieve adequate power for the primary objective of the study. In order to allow for the possibility of a small number of unevaluable patients, the accrual ceiling will be set at 36 patients.

If each patient has multiple and unequal number of benign lymph nodes and metastatic nodes, the linear mixed effects model will be used to model and test the difference of signal changes between benign lymph and metastatic nodes, where the random intercept is used to account for the within-patient correlation of signal changes of multiple nodes.

7.5 Analysis of Secondary Endpoints

The secondary endpoint of this study is to determine the most optimal timing for imaging: 24 hours vs. 48 hours post infusion.

One secondary objective of the study is to determine the most optimal timing for imaging: 24 hours vs. 48 hours post infusion. All the enrolled patients will be imaged at both time points post infusion, and signal change at both time points will be calculated. The time point with larger separation between metastatic and normal nodes with respect to post-infusion signal change will be considered the optimal timing for imaging.

Another second objective of the study is to use an ultrasound scan to evaluate visually (qualitatively) if there is agent uptake. The ultrasound scan will be done before infusion and 24 hours, 48 hours after infusions. This second objective is exploratory, and as such summary statistics such as the proportion of agent take at each time point and the corresponding standard error will be reported. In order to account for the intra-patient correlation of agent uptake of multiple nodes, the linear mixed effects model with the random intercept will be used to estimate the proportion of agent uptake at each time point.

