1 INTRODUCTION

1.1 Study Objectives

- 1.1.1 Primary Objective
- 1.1.1.1 To compare the difference in signal between metastatic and normal nodes in prostate, kidney and bladder cancer patients.
- 1.1.2 Secondary Objectives
- 1.1.2.1 To determine the most optimal timing for imaging: 24 hours vs. 48 hours post infusion
- 1.1.2.2 To determine the difference in signal within metastatic nodes in prostate, kidney, bladder cancer patients at ultrasonography.

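### Section 7.5 names the imaging time with the larger observed separation as optimal, with no measure of uncertainty, so a time is always named even when the data do not distinguish 24 h from 48 h.

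*Combined protocol and SAP*

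**What the plan says.** Section 1.1.2 lists the timing question first among the secondary objectives and words it as a determination: "To determine the most optimal timing for imaging: 24 hours vs. 48 hours post infusion". Section 7.5 describes the data, "All the enrolled patients will be imaged at both time points post infusion, and signal change at both time points will be calculated", and then the whole decision rule: "The time point with larger separation between metastatic and normal nodes with respect to post-infusion signal change will be considered the optimal timing". No interval, test, standard error or smallest relevant difference follows, and nothing says whether the choice is made per cancer or over all patients.

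No other section supplies these. Section 7.1 speaks of "determining the maximum difference per each imaging time point", which describes a measurement and not an inference. The paired t-test and mixed model in section 7.4 compare benign with metastatic nodes and contain no time term. The exploratory label in sections 7.1 and 7.5 applies to ultrasound only, and section 7.5 does plan a standard error and a mixed model for that ultrasound objective.

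**The concern.** Followed as written, the rule gives the same kind of statement (this time is optimal) whether the observed gap is large and consistent across patients or is no bigger than chance. A reader could not tell a trial that answered the question from one that did not.

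The question is a real one in the plan's own terms. Section 1.2.1 reports that an earlier ferumoxytol study in 10 prostate cancer patients saw the greatest contrast at 24 h, its last time point, with trends suggesting that later imaging might do better. Whether 48 h improves on 24 h, and by how much, is what the objective should settle. The paired scans already hold the information needed to put an interval on the answer.

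**Working it through.** **The plan's own figure first.** Section 7.4 gives the SD ("The standard deviation of signal change was similar for benign and malignant nodes and equaled 1.7 approximately"), assumes that "there is no correlation between benign lymph and metastatic node in pre-post ferumoxytol infusion signal change", and states: "With 10 patients for each cancer, the study has 93% power to detect a minimal mean signal change of three with the two-sided paired t-test".

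- SD of one patient's separation (benign minus metastatic signal change): 1.7 × √2 = 2.404.
- Two-sided 5% paired t-test, n = 10, 9 df, difference 3: power from the noncentral t is 93.8%. The stated 93% reproduces, so 2.404 is the SD the plan works with. The plan states no figure for 24 h versus 48 h.

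**The timing comparison.** Let D be a patient's separation at 48 h minus that at 24 h, and ρ the correlation between the two separations.

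- SD(D) = 2.404 × √(2(1 − ρ)); SE = SD(D)/√n.
- 95% CI half-width = t(0.975, n − 1) × SE.
- Probability of picking the wrong time when the true advantage is δ: Φ(−δ/SE).

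**Inputs not in the documents.** ρ is not given. I assume 0.5 to 0.8 and give the wider range 0 to 0.9 below. The values of δ are illustrations. For scale, section 7.4 expects a separation of 6.3 − 0.63 = 5.67, so δ = 0.25, 0.5 and 1.0 are about 4%, 9% and 18% of it. One benign and one metastatic node per patient is the plan's own sizing assumption.

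**Sample size.** The evaluable total is 50 (30/10/10) in the précis and section 7.1, but 30 in sections 4.1, 7.2 and 7.4. Because section 7.5 does not say pooled or per arm, n = 10, 30 and 50 are all shown. Ranges run from ρ = 0.8 to ρ = 0.5.

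| n | SE of mean D | 95% half-width | Wrong pick, δ = 0.25 | δ = 0.5 | δ = 1.0 |
|---|---|---|---|---|---|
| 50 | 0.215–0.340 | 0.43–0.68 | 12–23% | 1–7% | at most 0.2% |
| 30 | 0.278–0.439 | 0.57–0.90 | 18–28% | 4–13% | at most 1.1% |
| 10 | 0.481–0.760 | 1.09–1.72 | 30–37% | 15–26% | 2–9% |

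Example, n = 50, ρ = 0.5: SD(D) = 2.404 × √1 = 2.404; SE = 2.404/√50 = 0.340; half-width = 2.010 × 0.340 = 0.68; Φ(−0.25/0.340) = 23%.

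**Wider range, ρ from 0.9 down to 0.** Half-width is 0.31–0.97 at n = 50, 0.40–1.27 at n = 30 and 0.77–2.43 at n = 10. At δ = 0.5 the wrong-pick probability is 0.1–15%, 0.5–21% and 7–32%.

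**When the times are truly equal.** In 100,000 simulated trials at each n the written rule named a time every time, choosing each about half the time. The expected chance gap, SE × √(2/π), is 0.17–0.27 at n = 50 and 0.38–0.61 at n = 10 for ρ 0.8 to 0.5. A 95% CI on D excluded zero in about 5% of the same simulations.

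**The case against.** Choosing the larger estimate is a legitimate selection rule. If the two times are equal, either choice loses no separation, so always naming one is not a false-positive rate of 100%. **This stands.** A reader might infer that the rule is invalid or that its choice is usually noise; the table does not support that. For an advantage of 1.0 the rule is rarely wrong, and with 50 patients it is right in 93–99% of trials at 0.5. The larger error rates belong to small advantages, where a wrong pick costs least, or to a single 10-patient arm. What the objection does not answer is the reporting: section 7.5 gives no probability of correct selection, and a selection rule loses nothing by being shown with its interval.

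A reader might also conclude that a time should be called optimal only when the CI excludes zero. The documents do not require that, and it has a price. At a true advantage of 0.5, for ρ 0.5 to 0.8, such a gate would name a time in only about 30–63% of trials with 50 patients and 9–15% with 10. It would often leave the stated objective unanswered, so it is optional.

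Two further readings go beyond the text. Nothing in the documents says that the result will set imaging schedules in later work. Nor does the plan discard the pairing: it calculates signal change at both times for every patient, and does not define separation as a difference of two means. It is silent on the interval and does not rule one out.

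**Conclusion.** The concern holds as a gap in how the timing result is to be estimated and reported. That a time will always be named, with nothing planned to show how firmly the data support it, follows from section 7.5 alone and needs no numerical assumption.

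The size does rest on assumptions: SD 2.404 from section 7.4, one node of each class per patient, and ρ of 0.5 to 0.8. On those, the comparison is known to within about ±0.4–0.7 units with 50 patients, which is informative against an expected separation of 5.67, but only to within ±1.1–1.7 in one 10-patient arm. Whether the choice is pooled or per arm therefore matters a good deal, and the plan does not say. The primary comparison is unaffected.

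**What to change.** In section 7.5, make the 48 h minus 24 h difference in separation the reported quantity, with its 95% CI. Either of these would serve:

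- the mean of the per-patient paired differences; or
- the node-class-by-time contrast from a mixed model with node class, a time main effect, their interaction, and random effects for patient and for node. The model in section 7.4 has only a random intercept for within-patient correlation, and here the same node is measured twice.

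State whether the comparison is pooled over the three cancers, per arm, or both, and define separation for patients with several nodes. The time with the larger separation may still be named as preferred, provided it is reported with this interval. When the interval includes zero, the report must say that the data did not clearly distinguish the two times. A strict significance requirement before naming a time is optional.

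The cost is a few sentences and a modest extension of the model. No new scans or patients are needed. The downside is slightly more analysis and, in some outcomes, a less definite conclusion.

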5.3 Imaging Interpretation

The location of lymph nodes will be indicated on T1W, T2W and T2*W unenhanced MR images and the size of each node will be measured from the T1 images. Each visualized node will be assigned a number and a site (e.g. right, left, internal, external iliac, right left retroperitoneal). The location of the nodes will be transcribed to a map of the targeted region (chest, abdomen or pelvis). The map, nodal characterizations, and the MR images will be made available to the referring physician for reference. Signal intensity of visualized target lymph node will be recorded on unenhanced and 24 and 48 hours post Ferumoxytol infusion T2*W MR images by placing operator defined region-of-interest. Signal intensity changes will be measured between pre-infusion, 24 and 48 hours post Ferumoxytol infusion MR scans.

For the ultrasound imaging interpretation, the baseline and 24hour, 48hour post-infusion ultrasound images will be visually compared to monitor the signal changes.

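### Ultrasound uptake is a yes/no rating but gets a linear mixed model, so its promised standard error is wrong in a joint fit across times, and zero or undefined in separate fits at 0% or 100% uptake

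*Combined protocol and SAP*

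**What the plan says.** Section 7.5 (Analysis of Secondary Endpoints) sets a second secondary objective: to "use an ultrasound scan to evaluate visually (qualitatively) if there is agent uptake". On timing it says: "The ultrasound scan will be done before infusion and 24 hours, 48 hours after infusions". The output is described as follows: "summary statistics such as the proportion of agent take at each time point and the corresponding standard error will be reported". The method comes next, and the reason given for it is that nodes of the same patient are correlated: "the linear mixed effects model with the random intercept will be used to estimate the proportion of agent uptake at each time point".

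Section 5.3 confirms that there is no continuous ultrasound measurement: the baseline and "post-infusion ultrasound images will be visually compared to monitor the signal changes". Section 7.5 also gives the status of the analysis: "This second objective is exploratory".

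Section 7.4 uses the same model name for the MRI signal change, which is continuous. Nowhere do the documents name a logit link, a binomial family, GEE, an exact method, or a rule for a time point with 0% or 100% uptake. They do not say whether the time points share one model, or whether the arms are pooled.

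**The concern.** Allowing for several nodes per patient is the right aim. The difficulty is the distribution. A yes/no rating with uptake proportion p has variance p(1 − p), so its precision changes with p and vanishes at 0 and 1. A linear mixed model with a random intercept has one residual variance and one patient variance for all the data it is given.

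The time points are likely to differ in uptake. The first scan precedes any agent, so uptake near 0% is to be expected if that scan is rated at all. Section 4.4 limits ultrasound to accessible nodes, so the number of rated nodes may be small and extreme counts are plausible after infusion too.

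At stake is the only quantitative result planned for a listed secondary objective. A standard error of zero beside 0% would read as proof that no uptake occurs. A standard error borrowed from other time points would misstate how well each proportion is known.

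**Working it through.** **The plan's own figure.** The documents give no number for the ultrasound analysis, so there is none to reproduce. The 93% power in section 7.4 concerns the MRI comparison and plays no part here.

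**Inputs.** From the plan: a yes/no rating, three time points, a linear mixed model with a random patient intercept, and a standard error per time point. Assumed, because the documents do not give them for ultrasound: N = 30 patients, m = 2 nodes each, within-patient correlation ρ = 0.3, and uptake of 0%, 10% and 50% at the three scans. Section 7.4 expects at least 1–2 benign and 1–2 metastatic nodes per patient. Evaluable patients are given as 30 in sections 4.1, 7.2 and 7.4 and as 50 in section 7.1; the conclusion is the same for either.

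**Case 1: one model for all three times.**

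True variance of the observed proportion = p(1 − p)[1 + (m − 1)ρ] / (Nm).
- 0%: variance 0, standard error 0.
- 10%: 0.09 × 1.3 / 60 = 0.00195, standard error 0.044.
- 50%: 0.25 × 1.3 / 60 = 0.00542, standard error 0.074.

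The model pools the variance over times: (0 + 0.09 + 0.25) / 3 = 0.1133. It splits this into a patient part B and a residual part, and its squared standard error is B/30 + (0.1133 − B)/60 at every time.
- If ratings at different times are uncorrelated, B is the average covariance over the 15 pairs among a patient's six ratings: 0.3 × (0.09 + 0.25) / 15 = 0.0068. Then 0.0068/30 + 0.1065/60 = 0.00200, standard error 0.045.
- Over the wider range B = 0 to B = 0.3 × 0.1133, the standard error runs only from 0.043 to 0.050.

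So the model reports about 0.045 three times, where the truth is 0, 0.044 and 0.074. At 50% uptake the standard error is understated by about 39% (1 − 0.045/0.074). One simulation of this setting put the two non-zero true values at 0.043 and 0.080. The closed form is used here; a run of 20,000 simulated data sets agreed with it (0.044 and 0.073 to 0.074).

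A fitted example (10 patients, 2 nodes each, with 0, 5 and 7 of 20 nodes positive at the three scans) shows the same pattern: a standard error of 0.105 at all three times, including the scan where all 20 ratings are negative.

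**Case 2: a separate model for each time.**

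Away from the extremes this works. In a simulation with 2 nodes per patient and correlation 0.3, the model's standard error was 0.118 (10 patients, 30% uptake), 0.045 (30 patients, 10%) and 0.034 (50 patients, 10%). The formula above gives 0.117, 0.044 and 0.034.

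When all nodes at a time agree, both estimated variances are 0. The standard error is then 0 by formula, and the software used returned no value, for 10, 30 and 50 patients with 2 nodes each. The exact 95% upper limit for 0 of n, one node per patient, is 1 − 0.025^(1/n):
- n = 10: 30.8%
- n = 30: 11.6%
- n = 50: 7.1%

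**If an interval is added.** With 10 patients, 2 nodes each and 1 positive node, the fit gives 0.05 with standard error 0.05, so 0.05 ± 1.96 × 0.05 = −0.048 to 0.148. With 50 patients, 2 nodes each and 3 positive nodes in 2 patients, the fit is 0.030 with standard error 0.0222, giving about −0.014 to 0.074.

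**The case against.** The strongest reply is that this is a descriptive summary of an exploratory, visually read endpoint. The plan promises a standard error and names no interval, test or decision rule. Within a single time point every rating has the same marginal variance, so a random-intercept linear model has the right mean and covariance, and its standard error is about right. It also estimates the population proportion directly. A logistic model with a random intercept does not: with an assumed intercept standard deviation of 2, its back-transformed value turns a true 30% into about 20%, and 10% into about 3%. The ordinary binomial standard error is also zero at 0 of n, and logistic models break down there too. Finally, if uptake is read as change from baseline, as section 5.3 suggests, there may be no pre-infusion rating to model.

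Most of this stands, and it rules out three stronger readings that a reader might infer:
- That the plan will report limits outside 0 to 1. It will not unless someone builds a normal interval.
- That a linear model is wrong for any yes/no outcome. Separate fits at intermediate uptake are sound.
- That 0% before infusion is certain. It is expected, but a visual reader can err, and the scan may serve only as comparator.

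Poor coverage of a normal interval (65% at a true 10% uptake and 40% at 5%, for 10 independent ratings) is likewise not a property of the plan. It concerns an interval the plan does not name, at one node per patient and at uptake levels the documents do not give.

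The reply does not rescue the promised standard error in a joint fit, or in a separate fit at 0% or 100%. The plan neither excludes the first nor provides for the second.

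**Conclusion.** The point holds in limited form. As written, section 7.5 can yield a wrong standard error by either route. A joint fit gives one value for all times: about 0.045 where the true values are 0, 0.044 and 0.074, under the stated assumptions of 30 patients, 2 nodes each, correlation 0.3 and uptake 0/10/50%. Separate fits give zero or no value when the nodes all agree, although 0 of 10 leaves uptake of up to 31% open.

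The sizes are illustrative, since nodes per patient on ultrasound, their correlation and the uptake are all unknown. The direction is not: a single common variance cannot be right at several different proportions, and an estimated variance of zero cannot express the uncertainty in a small sample. The matter is worth correcting because it is cheap, but its weight is modest. The endpoint is exploratory, and the MRI primary analysis does not depend on it.

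**What to change.** In section 7.5, for the ultrasound objective:
- Replace the linear mixed model with a population-averaged logistic model (GEE clustered on patient, with a small-sample variance correction) for the 24 h and 48 h proportions. Report 95% limits computed on the logit scale and transformed back.
- When no node or every node shows uptake at a time point, report instead the number of patients with uptake and an exact binomial 95% interval, and state that the unit is then the patient.
- Treat the pre-infusion scan as the comparator for the later readings, and do not model a pre-infusion uptake proportion.

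The cost is a short rewording and slightly more analysis work, with no new data, patients or procedures. The drawback is the change of unit from node to patient in the fallback case, which has to be labelled wherever it is used.
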